### **7.3.1.1 Multiplicity adjustment**

There is one primary analysis variable. No multiplicity adjustment will be done among biomarkers. For the test groups compared to the reference groups for each biomarker, Dunnett's method will be used for the adjustment of multiple comparisons.

### **7.3.1.2 Dealing with non-normality**

A standard residual analysis using Proc Mixed procedure will be used to examine validity of normality assumptions for the primary endpoint. A natural logarithmic transformation might be applied to the endpoint in the linear mixed model with repeated measurements if the normality assumption does not hold. Square Root transformation will be used for urine mutagenicity statistical analysis.

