On each study day (Days 1 - 7), subjects in Group 1 will be allowed to smoke their OB cigarettes *ad libitum* (i.e., no restriction on the duration of use or the number of cigarettes per day) from 07:00 through 23:00. Subjects will be allowed to smoke upon request to the clinic staff but will only be allowed 1 cigarette at a time and will be instructed to return each cigarette butt upon completion.

On each study day (Days 1 - 7), subjects in Group 2 and Group 3 will smoke no more than 50% of their baseline CPD and will use the assigned VERVE® product *ad libitum* (i.e., no restrictions on the number of VERVE® products used at once, the number of VERVE® products used per day, or the duration of use) except for 3 specific VERVE® products use opportunities at approximately 11:00, 15:00, and 19:00 each day during which subjects will be asked to keep the assigned VERVE® product in their mouth for at least 10 minutes. Subjects will be allowed to smoke upon request to the clinic staff but will only be allowed 1 cigarette at a time and will be instructed to return each cigarette butt upon completion. Subjects will be allowed to use the VERVE® product upon request and they will be instructed to return each used VERVE® product upon completion.

On each study day (Days 1 - 7), subjects in Group 4 and Group 5 will use the assigned VERVE® product *ad libitum* (i.e., no restrictions on the number of VERVE® products used at once, the number of VERVE® products used per day, or the duration of use) except for 3 specific VERVE® products use opportunities at approximately 11:00, 15:00, and 19:00 each day during which subjects will be asked to keep the assigned VERVE® product in their mouth for at least 10 minutes. Subjects will be allowed to use the VERVE® product upon request and they will be instructed to return each used VERVE® product upon completion.

On each study day (Days 1 - 7), subjects in Group 6 will completely stop cigarette use and they will not be allowed to smoke or use VERVE® products.

All product use (CPD, VPD, number of VERVE® product per use, and VERVE® product use duration, [i.e., time of VERVE® product placement in the subjects' mouth, and time it was removed from the subjects' mouth], as appropriate) will be determined to assess product use behavior.

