### **11.9 Statistical Analysis**

Linear mixed models for ANCOVA will be used to compare the Day 5 and Day 7 biomarker values and subjective effects questionnaire scores between groups as described in the study objectives. In the statistical models, the outcome variable will be included as a dependent variable; group, and gender will be included as fixed effects; and baseline values/scores will be included as covariates. The SAS Proc Mixed procedure will be used. The LSM difference and 95% confidence interval for the LSM difference between the Test and Reference Groups will be provided.

Normality and equal variance assumptions will be tested for biomarker variables. An appropriate data transformation will be used if parametric assumptions for the distribution of above-mentioned data are markedly violated.

The statistical significance level will be 5% for two-sided testing. Adjustments for multiple comparisons will not be made.

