## 7.3 Statistical Analyses

### 7.3.1 Primary Endpoint Analysis

A linear mixed model for repeated measures (MMRM) analysis will be used for comparing each test group (Groups 2-5) to the control group (Group 1 and Group 6) in the primary endpoint (24-hour total urinary NNAL (mg/24 hours) excreted on Day 7). In the model, study group, study day, and study group by study day interaction, and gender are the fixed effect factors. The baseline value of the response biomarker is the covariate. A restricted maximum likelihood estimation method will be applied and several covariance structures will be tried. Five candidate covariance structures will be considered: compound symmetry, 1st order autoregressive, 1st order autoregressive with a random subject effect, unstructured and Toeplitz. The most appropriate covariance structure will be determined based on the AIC criteria (the covariance structure with the smallest AIC will be chosen). The least-square mean, 95% confidence interval and p-value will be provided for the study groups. The least-square mean difference, 95% confidence interval and p-value will be provided for the study group comparisons. Pairwise comparisons (Group 2 vs. Group 1, Group 3 vs. Group 1, Group 4 vs. Group 1, Group 5 vs. Group 1, Group 2 vs. Group 6, Group 3 vs. Group 6, Group 4 vs. Group 6, and Group 5 vs. Group 6,) will be performed using a Dunnett's test at a 2-sided significance level of 0.05 to adjust for multiplicity. Group 1 & 6 will be considered as the control groups. The test is for each of the other groups to compare with the control groups. The analysis will be conducted on the mITT and PP datasets.

The following SAS codes will be used to perform the analysis.

```
Proc mixed data=<>;
Class subject gender group day;
Model response = gender group day group*day baseline/ddfm=kr;
Repeated day/type=<type> subject=subject;
LSmeans group*day/CL alpha=0.05 pdiff dunnett ('1'*Day 7, '6'*Day 7);
```

Run;

Note: This model will include both the Day 7 value (primary endpoint) and interim time points (Day 5, secondary endpoint). The above analysis will also output the residual diagnosis to check for normality and to identify outliers).

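### The scale of the primary NNAL analysis is a discretionary choice made after residuals are seen, with no matching log of the Day -1 covariate and no ratio as the effect measure

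*SAP*

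**What the plan says.** - **Default model.** SAP 7.3.1 fits a repeated-measures model to 24-hour NNAL in all six groups, with one baseline slope. "The baseline value of the response biomarker is the covariate", and the code line is "Model response = gender group day group*day baseline/ddfm=kr". Both variable names are generic and neither is logged.
- **Fallback.** SAP 7.3.1.2: "A natural logarithmic transformation might be applied to the endpoint in the linear mixed model with repeated measurements", on the condition that normality fails. No test, threshold or decision-maker is given.
- **Scope of the check.** The residual analysis "will be used to examine validity of normality assumptions for the primary endpoint". Protocol 11.9 is broader: "Normality and equal variance assumptions will be tested for biomarker variables", with a suitable transformation to follow if the violation is marked. SAP Section 9 does not list a narrower scope among its changes from the protocol.
- **Mutagenicity.** "Square Root transformation will be used for urine mutagenicity statistical analysis". The scale of its baseline is not stated.
- **Effect measure.** SAP 7.3.1 and the comparison shells in Section 12 give LS means and LS mean differences, in ng/24 hour for NNAL. There is no ratio, geometric mean or back-transformation.

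**The concern.** The trial is open-label (Protocol 7.4), and the residuals come from the fitted primary model. Whether the main result is a difference in ng/24 hours or something on a log scale is therefore settled after the outcome has been modelled. Because the log step is permitted rather than required, either choice complies with the plan.

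The design gives a reason to expect the log scale to fit better. Protocol 3.1 states that "subjects in Group 2 and Group 3 will smoke no more than 50% of their baseline CPD". For smokers of 10-30 CPD, half is 5 to 15 cigarettes a day, so the imposed reduction scales with the subject's own baseline. If NNAL follows roughly in proportion, raw-scale baseline slopes and residual variances differ between groups, while SAP 7.3.1 fits one slope with no group-specific variance. On the log scale the groups are parallel.

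At stake are the precision and the error rate of the two comparisons that carry the hypothesis, Group 2 vs 1 and Group 3 vs 1. The secondary biomarkers use the same model through SAP 7.3.2.

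**Working it through.** **1. The plan's own figure.** SAP Section 4 gives 35 completers per group in Groups 1-3, 85% power, two-sided alpha 0.025. With n = 2(z₀.₉₈₇₅ + z₀.₈₅)²/d², 2(2.241 + 1.036)² = 21.5, and 21.5/35 = 0.614, so d = 0.784 (0.798 by the t test). The plan states no d, SD or correlation, so 35 can only be back-solved. Everything below therefore rests on assumed values.

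**2. Cost of a raw baseline with a ln endpoint.** Assume ln(Day 7) = ln(baseline) + group effect + error, with baseline log-SD s and residual log-SD r. The squared correlation between X and ln X for a log-normal X is s²/(e^(s²) − 1). Adjusting for X instead of ln X leaves extra residual variance s²[1 − s²/(e^(s²) − 1)]. The large-sample standard-error ratio, raw to ln baseline, is

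√{1 + s²[1 − s²/(e^(s²) − 1)]/r²}.

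With s = 0.9 and r = 0.25: s² = 0.81; e^0.81 − 1 = 1.248; 1 − 0.81/1.248 = 0.351; 0.81 × 0.351 = 0.284; √(1 + 0.284/0.0625) = 2.36. Baseline correlation is s/√(s² + r²) = 0.9/0.934 = 0.96.

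**3. Power.** Monte Carlo Day 7 ANCOVA with gender and baseline; 35/35/35/25/25/25 completers (SAP Section 4); Groups 4-6 at ratio 0.55; Group 2 vs 1 at two-sided 0.025; 4,000 runs. Day 5, the repeated-measures covariance and Dunnett are left out.

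| s | r | Group 2/1 ratio | Correlation | Power, raw/raw | Power, ln/ln | Power, ln with raw baseline | SE ratio (formula) |
|---|---|---|---|---|---|---|---|
| 0.5 | 0.25 | 0.80 | 0.89 | 87% | 93% | 79% | 1.22 |
| 0.7 | 0.25 | 0.80 | 0.94 | 77% | 92% | 51% | 1.66 |
| 0.9 | 0.25 | 0.80 | 0.96 | 62% | 92% | 29% | 2.36 |
| 0.5 | 0.40 | 0.70 | 0.78 | 89% | 92% | 87% | 1.09 |
| 0.7 | 0.40 | 0.70 | 0.87 | 80% | 92% | 74% | 1.30 |
| 0.9 | 0.40 | 0.70 | 0.91 | 70% | 93% | 54% | 1.67 |

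In simulation at these sample sizes the SE ratio ran from 1.08 to 2.23, slightly below the large-sample formula at the top end.

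**4. Type I error of the raw model.** With no Group 2 effect, the raw six-group model rejected in 3.7-5.1% of runs with Groups 4-6 at ratio 0.55, and in 4.4-6.4% across six other settings with ratio 0.3. A further run gave 3.2-6.0%. Nominal is 2.5%. The ln models stayed at about 2-3%. With Groups 1 and 2 alone, the raw model rejected in 1.6-2.2%. The excess therefore comes from pooling: Groups 4-6 have lower raw-scale variance and shrink the error term used for Group 2 vs 1.

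**5. Where the ordering changes.** These cells bear on the fallback against the raw model:

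- Six groups, s = r = 0.5 (correlation 0.71), ratio 0.65: ln with raw baseline 88%, raw 86%.
- Six groups, s = r = 0.7 (correlation 0.71), ratio 0.55: 83% against 73%.
- Groups 1 and 2 alone, log-SD 0.8, correlation 0.7, ratio 0.65: 72% against 59%.

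This one bears on raw against ln/ln:

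- Six groups, log-SD 0.4, correlation 0.3, log-scale baseline slope equal to the correlation instead of 1: raw 94.6%, ln/ln 88.5%. With Groups 1 and 2 alone, where the raw model's error is not inflated, the order is 84.2% against 88.0%.

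**The case against.** The strongest reply is that this is mostly silence, not error.

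- **The covariate.** If the response is ln NNAL, the baseline value of the response can naturally be read as ln baseline. That is fair: no sentence says that baseline stays raw. A raw baseline is the literal reading, since only the endpoint is named, but not the only one. Step 2 measures the cost of that reading.
- **Power of the fallback.** A reader might infer from the table that the fallback is weaker than not transforming at all. The documents do not support this. They give no SD, correlation or effect size; the table covers correlations of 0.78-0.96 with a log slope of exactly 1; step 5 shows reversals; and part of the raw model's power is inflated error.
- **Secondary biomarkers.** A reader might infer that they go unchecked. That is too strong. Protocol 11.9 covers biomarker variables, the note to SAP 7.3.1 outputs residual diagnostics, SAP 7.3.2 reuses the model, and mutagenicity has its own transformation. What stands is that SAP 7.3.1.2 names only the primary endpoint and does not say that its rule carries over.
- **Estimand and shells.** A difference in ng/24 hours is a legitimate effect measure and matches the declared outcome, and SAP Section 12 says that shells may change. Neither point fixes the scale in advance.
- **Proportionality.** The CPD limit is a maximum, and the documents do not show that NNAL falls in proportion to it. This stands as a limit on the size of the effect.

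**Conclusion.** The point holds as a defect of pre-specification with a better method available. The scale of the primary analysis is left to a discretionary decision after residuals are seen, the baseline is not tied to the scale of the endpoint, and no effect measure suits a log analysis.

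If NNAL is log-normal with a roughly proportional effect, the default raw-scale model has less power than ln/ln (62-89% against 92-93% in the table) and can exceed its nominal error for Group 2 vs 1 (about 3-6% against 2.5%). Under the literal fallback, the standard error is about 1.1 times that with a ln baseline at correlation 0.6-0.8, and up to 2.2 times at 0.96. Across all settings tried, ln/ln was at least as powerful as ln with a raw baseline, within simulation error.

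The direction of that last comparison is robust; its size is not known from the documents. Whether the fallback beats or loses to the raw model depends on the correlation and effect size, and no claim is made on it.

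**What to change.** In SAP 7.3.1 and 7.3.1.2:

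1. Make ln(24-hour NNAL) the response and ln(Day -1 NNAL) the covariate of the primary analysis, without a residual trigger.
2. Report ratios of geometric LS means with back-transformed Dunnett intervals, and change the NNAL comparison shells to match.
3. Keep the raw-scale model as a named sensitivity analysis.
4. State that whenever a biomarker is transformed, its baseline gets the same transformation. This includes square-root mutagenicity.
5. State that the residual check and transformation rule cover the secondary biomarkers, as in Protocol 11.9. Do not log all of them and COHb by rule: where many values are below quantitation, half-LLOQ substitution could cluster the lower tail on the log scale.

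The cost is SAP wording and shell edits, with no new data or subjects. The downside is that the headline effect becomes a ratio instead of a difference in ng/24 hours; the raw-scale sensitivity analysis still supplies the difference.

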## **7.3.2 Secondary Endpoint Analysis**

The same statistical analysis model defined in the primary analysis Section 7.3.1 will also be used to make same comparisons as the primary endpoint (i.e. total NNAL on Day 7) for the secondary biomarker endpoints listed in Section 2.4.

These analyses will be conducted on the mITT and PP datasets.

## **7.3.3 Subjective Effects**

Similar statistical comparison analysis (defined in 7.3.1) will be preformed on QSU-brief change from pre-use score and mCEQ original scores (mCEQ-C, among Group 1, 2, and 3; mCEQ-V, among Groups 2, 3, 4, and 5). The comparisons interested for QSU-brief will be the test groups (Groups 2-5) versus the continue smoking group (Group 1) and test groups (Groups 2-5) versus the tobacco cessation Group. The comparisons interested for mCEQ-C will be the dual use groups (Groups 2-3) versus the continue smoking group (Group 1). The comparisons interested for mCEQ-V will be the dual use groups (Groups 2-3) versus the exclusive use group (Groups 4 -5) [i.e. Group 2 vs Group 4 and Group 3 vs Group 5].

This analysis will be conducted on the mITT datasets. No multiple adjustment will be performed for subject effect scores.

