## **7.8 Blood Sample Collection and Processing**

A blood sample for COHb will be collected on Days -1, 5 and 7 between 15 minutes to 45 minutes following the start of subject's in the moment subjective questionnaires scheduled for at 21:30. Subjects will abstain from product use, as appropriate, for at least 15 minutes prior to blood draw for COHb.

Samples for COHb will be collected into two 4 mL sodium heparin vacutainers. Immediately following collection, the blood samples will be gently inverted to mix. The whole blood samples will be stored at  $5^{\circ}\text{C}$  ( $\pm 3^{\circ}\text{C}$ ) until shipped to Celerion Bioanalytical Services (Lincoln, Nebraska) for analysis. Additional instructions for blood sample collection, processing, and shipping will be provided separately.

For all schedules samples for COHb, approximately 8 mL of blood will be collected from each subject.

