### Modified Intent-to-Treat (MITT) Dataset:

All randomized subjects who have a valid baseline and post-baseline endpoint value (total NNAL). This population will be used for primary endpoints analysis.

Per-Protocol (PP) Dataset:

A subset of the MITT dataset and includes subjects who completed the study without major protocol deviations that are considered to impact data integrity (e.g., non-adherence to study group assignment).

If it is determined that a subject was pregnant during the study, all of the pregnant subject's data will be reported, but will be excluded from summarization and statistical analyses.

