### **Secondary**

The secondary outcome variables are:

- 24-hour urinary total total NNN, NE, 2-AN, 4-ABP, HEMA, CEMA, S-PMA, 3-HMPMA, 3-HPMA, 2-HPMA, AAMA, GAMA, 2-MHBMA, 2-OHFle, 2-Naphthol, 1-OHPhe, mutagenicity, and 1-OHP excreted on Day 5 and Day 7.
- 24-hour urinary total NNAL excreted on Day 5.
- COHb on Day 5 and Day 7.
- QSU-Brief responses and factor scores on Day 1, Day 5, and Day 7.
- Responses to the appropriate mCEQ on Day 1, Day 5, and Day 7.
- Responses to the appropriate Use the Product Again questionnaire on Day 7.
- Product use behavior daily from Day 1 to Day 7 (i.e., CPD, VPD, and the average and total duration of VERVE® product use each day).

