### **Modified Intent-to-Treat (mITT) Dataset:**

All randomized subjects who used at least one study product after randomization (except Group 6) and have a valid baseline and at least one post-baseline biomarker measure of any one biomarker.

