## 7. BIOMARKER ASSESSMENT AND ANALYSIS

### 7.1 Biomarkers Sample Collection and Measurements

#### 7.1.1 Urine Biomarkers of Exposure (BOE)

##### 7.1.1.1 Urine BOE Sample Collection

24-hour urine collections for biomarkers of exposure (total NNAL, total NNN, NE, 2-AN, 4-ABP, HEMA, CEMA, S-PMA, 3-HMPMA, 3-HPMA, 2-HPMA, AAMA, GAMA, 2-MHBMA, 2-OHFle, 2-Naphthol, 1-OHPhe, mutagenicity, and 1-OHP) will be performed on Days -1, 5, and 7. Urine creatinine will be measured in each 24-hour collection and will be used to adjust the concentration values of urine biomarkers. Each 24-hour urine collection will be from approximately ( $\pm$  30 minutes) 07:00 on the scheduled day to approximately 07:00 the following day. The 24-hour urine collection begins on each scheduled day after the first morning void and any void prior to 07:00, and finishes the following morning with the last void collected at approximately 07:00 (including first morning void). Subjects will be specifically instructed to collect all urine voided, and any missed collection during the 24-hour interval will be documented as a deviation.

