### 7.2.5 Product Use

#### Product Use

Number of CPD smoked per day (Groups 1, 2, and 3, only), number of VPD per day (Groups 2, 3, 4, and 5 only), average duration of VERVE® product used per use each day (Groups 2, 3, 4, and 5 only), and total duration of VERVE® product use per Day (Groups 2, 3, 4, and 5 only) will be listed by subject and study day and summarized by group and study day using descriptive statistics (n, n missing, mean, SD, CV%, SEM, minimum, Q1, median, Q3, maximum and 95% CI). The start time of VERVE producct use along time of the day (x-axis, 7:00 to 23:00) by group (y-axis, Group 2, 3, 4, 5) for Day 1, 5, 7 (one plot per day) will be plotted.

Product use analyses will be performed on the mITT dataset.

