### 7.2.6 Questionnaires

The responses and the factor scores from the QSU-Brief will be listed by subject, study day and collection time. Factor scores (original scores, and change from pre-use scores) will be summarized by group, day and collection time using descriptive statistics (n, n missing, mean, SD, CV%, SEM, minimum, Q1, median, Q3, maximum, and 95% CI).

The mCEQ will be considered as a 7-point scale and treated as a continuous variable. The responses from mCEQ-C or mCEQ-V and factor scores will be listed by subject and study day. The factor scores will be summarized by group and study day using descriptive statistics (n, n missing, mean, SD, CV%, SEM, minimum, Q1, median, Q3, maximum and 95% CI).

Responses to Use the Product Again questionnaire recorded as VAS scores will be treated as bipolar variable and summarized by study group, study product and category using frequency count tables. The original response VAS score and bipolar score for the Use the Product Again questionnaire will be summarized using descriptive statistics (n, n missing, mean, SD, CV%, SEM, minimum, Q1, median, Q3, maximum and 95% CI).

These analyses will be performed on the mITT dataset.

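### Product-use, QSU-Brief and mCEQ analyses require a biomarker that first exists on Day 5, so early leavers' Day 1 scores and Day 1-4 use data drop out of the summaries and models

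*SAP*

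**What the plan says.** SAP 7.3.3 assigns the inferential comparisons of QSU-Brief and mCEQ to one set: "This analysis will be conducted on the mITT datasets". SAP 7.2.6 does so for the questionnaire summaries ("These analyses will be performed on the mITT dataset") and SAP 7.2.5 for product use ("Product use analyses will be performed on the mITT dataset"). The titles of Tables 14.2.2.x and 14.2.3.x name the same population and no other.

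SAP 5 defines mITT. Besides randomization and, outside Group 6, some product use, subjects must "have a valid baseline and at least one post-baseline biomarker measure of any one biomarker".

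SAP 7.1.1.1 says that the urine collections "will be performed on Days -1, 5, and 7". Protocol 7.8 gives the same days for carboxyhemoglobin: "A blood sample for COHb will be collected on Days -1, 5 and 7". For subjects who terminate early, Protocol 9 asks for the end-of-study safety data and specifies no biomarker sample.

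The outcomes concerned start earlier. SAP 2.4 lists "QSU-Brief responses and factor scores on Day 1, Day 5, and Day 7" among the secondary outcomes, with mCEQ on the same days and product use daily from Day 1. Secondary objective 6 includes Day 1 among its comparison days.

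Protocol 11.3 defines its MITT set by total NNAL and adds "This population will be used for primary endpoints analysis". It names no population for questionnaires or product use.

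**The concern.** Whether someone has a Day 5 urine or blood sample has no bearing on whether a Day 1 urge score or a Day 2 count of VERVE pieces is valid. Yet that sample decides whether those data are analysed.

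Two things are at stake. First, the Day 1 comparisons are restricted to people who stayed until Day 5. Staying comes after the Day 1 outcome and may well depend on it, since subjects with strong urges or little liking for the product could be readier to leave. Groups differ in how restricted they are: Group 1 smokes freely, Groups 2 and 3 are capped, and Groups 4 to 6 may not smoke. Departure need not be balanced, so randomization no longer protects the Day 1 contrasts.

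Second, the shells for the QSU-Brief and mCEQ models use Days 1, 5 and 7. A likelihood-based repeated-measures model that keeps a leaver's Day 1 score uses its correlation with the later days and, under missing at random, adjusts the Day 5 and Day 7 estimates. Removing the subject discards that information.

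Nothing planned would reveal the effect. SAP 7.3.4.1 confines sensitivity analyses to the primary endpoint. The biomarkers are analysed on both mITT and per-protocol sets; the questionnaires and product use are analysed on mITT alone.

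**Working it through.** The plan states no figure for this exclusion, so there is none to reproduce. The check traces the mITT definition against the schedule and then bounds the numbers.

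**Step 1: earliest qualifying biomarker.** The Day 5 urine collection runs from about 07:00 on Day 5 to about 07:00 on Day 6. The Day 5 COHb sample follows the questionnaires scheduled for 21:30. No biomarker is scheduled between Day 1 and Day 4, and none at early termination.

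**Step 2: what exists by then.** The QSU-Brief analysis variable in SAP 7.1.4.2 is the evening score minus the morning score, so it needs the 21:30 assessment. mCEQ is given only at 21:30.

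| Subject leaves | QSU-Brief change | mCEQ (Groups 1-5) | Product use (Groups 1-5) |
|---|---|---|---|
| Day 1, before the evening assessments | none exists | none exists | part of Day 1 omitted |
| After the Day 1 evening assessments, through Day 4 | Day 1 omitted | Day 1 omitted | up to four days omitted |
| Day 5, before a valid sample | Day 1 omitted | Day 1 omitted | Days 1-4 and part of Day 5 omitted |

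Group 6 has no on-study product use and no post-baseline mCEQ, so it can lose only QSU-Brief data. Use the Product Again is asked only on Day 7, so a subject who leaves before Day 5 has no such response to lose.

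**Step 3: which comparisons are touched (SAP 7.3.3).**
- QSU-Brief: Groups 2-5 against Group 1, and Groups 2-5 against Group 6.
- mCEQ-C: Groups 2 and 3 against Group 1.
- mCEQ-V: Group 2 against Group 4, and Group 3 against Group 5.
- Product use: descriptive summaries only, with no between-group test.

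**Step 4: how many subjects.** Inputs are the group sizes (SAP 3) and the completers needed (SAP 4).
- Groups 1-3: 40 − 35 = 5 per group; 5/40 = 12.5%.
- Groups 4-6: 30 − 25 = 5 per group; 5/30 = 16.7%.
- Overall: 6 × 5 = 30; 30/210 = 14.3%.

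This headroom covers dropout through completion, and the plan does not say how much falls before Day 5. The affected number is therefore 0 to 5 per group.

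**Step 5: illustration of size (assumption).** If k of n subjects leave, the full-group mean differs from the stayers' mean by (k/n) × (leavers' mean − stayers' mean). The documents give no difference between leavers and stayers. Suppose it is 0.25 to 1.0 SD on the analysed variable, and all five leave early:
- n = 40: 0.125 × 0.25 = 0.03 SD to 0.125 × 1.0 = 0.125 SD.
- n = 30: 0.167 × 0.25 = 0.04 SD to 0.167 × 1.0 = 0.17 SD.

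A contrast is biased by the difference between the two groups' shifts. For mCEQ-V, Group 4 against Group 2, equal losses of five with the same 1.0 SD difference give 0.167 − 0.125 = 0.04 SD. Losses in Group 4 alone give 0.17 SD. With no early leavers the bias is zero.

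**The case against.** The strongest reply is that few subjects will be affected. They are confined from Day -3. Anyone unwilling to use or unable to tolerate all four VERVE products leaves at the product trial, before randomization, and eligibility requires being willing and able to abstain. Withdrawn subjects may be replaced. The outcomes are secondary and carry no multiplicity adjustment, and the primary NNAL hypothesis is untouched. The SAP also relaxed the protocol's condition from an NNAL value to any one biomarker, which admits more people.

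Most of this stands as a limit on size: the number may be small or zero. It does not justify the condition. Replacement restores the count but not the composition of the group, and no argument links a biomarker to the validity of a questionnaire or use record.

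A reader might also infer that the SAP contradicts the protocol by taking MITT beyond the primary endpoint. The documents do not support that. Protocol 11.3 says what MITT is for but does not say it is for nothing else, and Protocol 11.1 leaves analysis details to the SAP. The SAP fills a gap here. It remains true that SAP 9 mentions neither the changed definition nor its use for these endpoints.

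**Conclusion.** The exclusion follows directly from the SAP's own text and affects declared outcomes: the Day 1 QSU-Brief and mCEQ comparisons and the Day 1-4 product-use summaries. It selects on a later, plausibly related event and discards usable Day 1 information. It reaches 0 to 5 subjects per group within the plan's allowance, at most 12.5% in Groups 1-3 and 16.7% in Groups 4-6, and the maximum holds only if all allowed dropout precedes the Day 5 sample. The shifts in SD units rest on an assumed difference between leavers and stayers.

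Two stronger readings should be resisted. One is that the rule favours VERVE and abstinence over continued smoking. No Group 6 against Group 1 comparison is planned, and Group 6 serves only as a reference, so selective loss there could work against VERVE. The mCEQ-V contrasts have a VERVE group on both sides. For QSU-Brief the analysed variable is a within-day change, and a subject with persistently strong urges can have a change near zero. The direction is open. The other is that data are deleted. They are omitted from summaries and models, but SAP 7.2.5 and 7.2.6 still list them by subject.

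This is a sound correction to make for secondary objectives. It is not a threat to the primary result.

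**What to change.** In SAP 5, define a questionnaire/product-use set: all randomized subjects with one or more relevant questionnaire or product-use records after randomization, analysed as randomized, with no biomarker requirement. Name it in SAP 7.2.5, in 7.2.6 for QSU-Brief and mCEQ, and in 7.3.3, and in the titles of Tables 14.2.2.x, 14.2.3.1.x and 14.2.3.2.x. Keep mITT as the supportive set and record the new set in SAP 9. The planned repeated-measures model already accommodates subjects without Day 5 and Day 7 scores, so its specification need not change. The Use the Product Again tables (14.2.3.3.x) can stay as they are, since they gain nothing for subjects who leave before Day 5.

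The cost is a few lines of SAP text, the table titles, and a repeat run of the affected tables on mITT. No new data are needed.
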